8.2 Main trial outcomes

All the outcomes listed in this section are in line with IMMPACT consensus recommendations for interpreting the clinical importance of treatment outcomes in clinical trials of the efficacy and effectiveness of chronic pain treatments [45]. IMMPACT highlights 4 core domains:

1. Pain intensity, assessed by a 0 to 10 NRS
2. Physical functioning
3. Emotional functioning
4. Participant ratings of overall improvement, assessed by the PGIC and Clinician Global Impression of Change (CGIC) with a 7 point Likert scale.

8.3 Primary outcome

7-day average 24-hour pain on an 11-point NRS scale (0 = no pain and 10 = worst pain imaginable) measured at 3 months post-randomisation.

8.4 Secondary outcomes

8.4.1 Clinical

1. 7-day average 24-hour pain on an 11-point NRS scale (0 = no pain and 10 = worst pain imaginable) measured at the end of treatment) and at 6 months.
2. Neuropathic Pain Impact on Quality-of-Life Questionnaire (NePIQoL) as a measure of disease specific quality of life at 3 and 6 months.
3. Treatment success (measured as a 30% reduction in 7-day average 24-hour pain scores) at end of treatment, 3 months and 6 months.
4. Treatment success (measured as a 50% reduction in 7-day average 24-hour pain scores) at end of treatment, 3 months and 6 months.
5. Area Under the Curve (AUC) for the daily NRS pain scores over the study period (from baseline to 3 months and from baseline to 6 months)
6. Brief Pain Inventory-Diabetic Peripheral Neuropathy (BPI-DPN) as a measure of pain interference with function total score at 3 and 6 months.
7. Beck Depression Inventory as a measure of depression at 3 and 6 months.
8. Pittsburgh Sleep Quality Index (PSQI) as a general measure of sleep quality at 3 and 6 months.
9. Patient and Clinician Global Impression of Change at end of treatment, 3 months and 6 months.
10. Changes to pain medications (frequencies and dosages) at 3 and 6 months.
11. Patient perception of their treatment arm at the end of the treatment phase.

8.4.1 Cost-Effectiveness

1. Health-related QoL at 6 months assessed by the EuroQoL-5D-5L.
2. Health resource use at 3 and 6 months.
3. Cost per quality adjusted life year (QALY) gained over 6 months.

8.4.2 Safety

3. Frequency and proportion of Adverse Events.
4. Frequency of Serious Adverse Events.

8.4.3 Subgroup outcomes

The NPSI questionnaire will be used for subgroup analysis relating pain phenotype to treatment response [75]. There is emerging evidence that treatment response may be determined by a patient's pain phenotype [76-78]. In particular, these outcomes will be evaluated:

1. "Burning (superficial) spontaneous pain" NPSI mean subscores at end of treatment, 3 months and 6 months.
2. "Pressing (deep) spontaneous pain" NPSI mean subscores at end of treatment, 3 months and 6 months.
3. "Paroxysmal pain" NPSI mean subscores at end of treatment, 3 months and 6 months.
4. "Evoked pain" NPSI mean subscores at end of treatment, 3 months and 6 months.
5. "Paresthesia/dysesthesia" NPSI mean subscores at end of treatment, 3 months and 6 months.
6. NPSI mean total score at end of treatment, 3 months and 6 months.

8.5 Safety sub study

This sub study is aimed at ensuring that there is no worsening sensory dysfunction with the trial interventions. This sub study will perform QST using the validated and standardised DFNS protocol, which has validated age and gender at birth normative values [67]. The DFNS has been shown to have good inter-observer and test-retest reliability for use in patients with sensory disturbances of different aetiologies to help identify mechanisms of neuropathic pain [68]. The DFNS protocol takes 60 minutes to perform and will only be conducted in two trial centres, Sheffield and Liverpool, as the PIs in these

centres have been trained in the use of the DFNS. The DFNS will be performed at baseline and 3 months. This sub study will ensure the safety of FREMS treatment by examining for any changes in QST (including sensory perception of sharp, cold, warm, or vibration stimuli) during the trial as performed in previous trials [69].

9. TRIAL PROCEDURES

The intervention (FREMS or TENS) will be delivered by a research nurse or a health care assistant.

For trial assessments please see Table 5. The trial visits and data collected are summarised below:

Visit -1: Remote screening consent for potentially eligible patients followed by 1 week of daily NRS to assess eligibility based on a mean pain severity score of 4 and above. The daily NRS will be collected via text message or email during this period and throughout trial follow up if the participant is subsequently randomised into the trial.

Visit 0: Trial eligibility and consent, randomisation and collection of baseline data. All the data required to assess eligibility will be collected. In addition, other essential data for the trial will be collected including age, ethnicity, gender at birth, diabetes type, diabetes duration, medications history, past medical history, smoking history, alcohol intake, blood pressure, weight, height.

Visit 1-10: 10 FREMS or TENS sessions over 2 weeks, 35 minutes each. For data collected at visit 10 (End of treatment), please see Table 5.

Visits 11-12: At 3 and 6 months respectively. For assessments please see Table 5.

Long-term follow up: Participant consent will be sought to access routinely collected NHS data to assess health resource usage beyond the end of this trial as per section 4.3.

NB: it is expected that in most cases Visits 0 and 1 will be combined in order to start treatment on the day of randomisation.

9.1 Schedule of assessments

Table 5: Schedule of Assessments

Assessment	Screening (visit -1)	Baseline (visit 0)	End of treatment (visit 10)	3 months post- randomisation (visit 11)	6 months post- randomisation (visit 12)
Informed consent	X	X			
Eligibility checked	X	X			
NRS*	X	X	X	X	X
MNSI		X			X**
DN-4		X			
NPSI		X	X	X	X
Medications		X		X	X
Patient GIC			X	X	X
Clinician GIC			X	X	X
Beck Depression Inventory		X		X	X
EQ5D-5L		X		X	X
NePIQoL		X		X	X
PSQI		X		X	X
BPI-DPN		X		X	X
HbA1c if not done in the last 2 months		X			
Medical history and examination		X			X
Health resource usage				X	X
DFNS quantitative sensory testing**		X		X	X
AE review			X	X	X

NRS:* collected daily via text messages or emails and the average of the last 7 days will be calculated at each time point.

***:* These will be performed to ensure no worsening neuropathy in selected centres only.

9.2 Withdrawal and changes in levels of participation

Informed consent is defined as the process of learning the key facts about a clinical trial before deciding whether or not to participate. It is a continuous and dynamic process and participants should be asked about their ongoing willingness to continue participation at all visits. Participants should be aware from the beginning that they can freely withdraw (cease to participate) from the trial at any time. A participant may wish to cease to participate in a *particular* aspect of the trial.

Participants found to be ineligible post-randomisation should be followed up according to all trial processes and will still have their data analysed unless they explicitly change their level of participation.

The changes in levels of participation within the trial are categorised in the following ways:

No trial intervention: The participant would no longer like to receive the trial intervention but is willing to be followed up in accordance with the schedule of assessments and if applicable using any central UK NHS bodies for long-term outcomes (i.e. the participant has agreed that data can be collected and used in the trial analysis).

No trial related follow-up: The participant does not wish to attend trial visits in accordance with the schedule of assessments but is willing to be followed up at standard clinic visits and if applicable using any central UK NHS bodies for long-term outcomes (i.e. the participant has agreed that data can be collected at standard clinic visits and used in the trial analysis, including data collected as part of long-term outcomes).

No further data collection: The participant is not willing to be followed up in any way for the purposes of the trial AND does not wish for any further data to be collected (i.e. only data collected prior to any changes of levels in participation can be used in the trial analysis).

The details of changes of levels in participation within trial (date, reason and category of status change) should be clearly documented in the source documents.

10. ADVERSE EVENTS REPORTING

10.1 Definitions

Table 6: Adverse event reporting definitions

Severity Definitions	Mild	Awareness of signs or symptoms that do not interfere with the participant’s usual activity or are transient and resolved without treatment and with no sequelae.
	Moderate	A sign or symptom, which interferes with the participant’s usual activity.
	Severe	Incapacity with inability to do work or perform usual activities.
Adverse Event	AE	Any untoward medical occurrence in a participant participating in the trial which does not necessarily have a causal relationship with the intervention received.
Related Event	RE	An event which resulted from the administration of any of the research procedures.
Serious Adverse Event	SAE	An untoward occurrence that: Results in death Is life-threatening* Requires hospitalisation or prolongation of existing hospitalisation Results in persistent or significant disability or incapacity Consists of a congenital anomaly/ birth defect

		Or is otherwise considered medically significant by the Investigator**
Unexpected Event	UE	The type of event that is not listed in the protocol as an expected occurrence.
Related and Unexpected Serious Adverse Event	N/A	A SAE that meets both the definition of a Related and Unexpected Event.

* The term *life-threatening* is defined as diseases or conditions where the likelihood of death is high unless the course of the disease is interrupted.

** Medical events that may not be immediately life-threatening or result in death or hospitalisation but may jeopardise the participant or may require intervention to prevent one of the other outcomes listed in the definitions above.

10.2 Adverse event recording – general

The recording and reporting of Adverse Events (AEs) will be in accordance with the UK Policy Framework for Health and Social Care Research, the Principles of GCP as set out in the UK Statutory Instrument (2004/1031; and subsequent amendments) and the requirements of the Health Research Authority (HRA). Definitions for adverse event reporting are listed in **Table 6: Adverse event reporting definitions** in Section 10.1.

It is routine practice to record AEs in the participant's medical notes and it is also recommended that this includes the documentation of the assessment of severity and seriousness and also of causality (relatedness) in relation to the intervention(s) in accordance with the protocol.

10.3 AE reporting in FREMS-PDPN

The reporting period for AEs in FREMS-PDPN will be from the start of treatment until the end of trial follow-up.

The safety profile for this trial population and interventions are well characterised so a strategy of targeted reporting of AEs will not affect the safety of participants. Only those AEs detailed below will be reported:

- Serious Adverse Events (SAEs) (reported on trial specific SAE CRF).
- AEs possibly or definitely related to trial treatment, occurring between the start of trial treatment and 7 days after the end of the trial treatment period (reported on trial specific AE log).

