10.6 Assessment of causality of an SAE

When completing the SAE form, the PI (or, throughout this section, a medically qualified delegate) will be asked to define the nature of the seriousness and causality (relatedness; see Table 7: Categories of causality) of the event.

In defining the causality the PI must consider if any concomitant events or medications may have contributed to the event and, where this is so, these events or medications should be reported on the SAE form. It is not necessary to report concomitant events or medications which did not contribute to the event.

As per **Table 7**, all events considered to be ‘possibly’, ‘probably’, or ‘definitely’ related to the intervention will be reported by the Trial Office as ‘related’; all events considered at site to be ‘unlikely’ or ‘unrelated’ to the intervention will be reported by the Trial Office as ‘unrelated’. The same categorisation should be used when describing AEs and protocol-exempt SAEs in the source data.

Table 7: Categories of causality

Category	Definition	Causality
Definitely	There is clear evidence to suggest a causal relationship, and other possible contributing factors can be ruled out.	Related
Probably	There is evidence to suggest a causal relationship, and the influence of other factors is unlikely.	
Possibly	There is some evidence to suggest a causal relationship. However, the influence of other factors may have contributed to the event (e.g. the participant’s clinical condition, other concomitant events or medication)	
Unlikely	There is little evidence to suggest there is a causal relationship. There is another reasonable explanation for the event (e.g. the participant’s clinical condition, other concomitant events or medication).	Unrelated
Not related	There is no evidence of any causal relationship.	

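### Section 10.3 leaves the 'probably related' grade out of its closed list of reportable non-serious AEs, contradicting Table 7, and does not say which reporting period applies to which type of event

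*Protocol*

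**What the plan says.** Section 10.3 first sets a general period: "The reporting period for AEs in FREMS-PDPN will be from the start of treatment until the end of trial follow-up". It then adopts targeted reporting, on the ground that "a strategy of targeted reporting of AEs will not affect the safety of participants", and closes the list with "Only those AEs detailed below will be reported". The list has two entries:

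- "Serious Adverse Events (SAEs) (reported on trial specific SAE CRF"), with no causality condition and no time limit of its own;
- "AEs possibly or definitely related to trial treatment, occurring between the start of trial treatment and 7 days after the end", meaning when the course of sessions finishes; these go on the AE log.

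Section 10.6 and Table 7 define five causality grades. On how they are grouped, the section says that "all events considered to be ‘possibly’, ‘probably’, or ‘definitely’ related to the intervention will be reported by the Trial Office as ‘related"; the two lower grades count as unrelated. It then extends the scale beyond SAEs: "The same categorisation should be used when describing AEs and protocol-exempt SAEs in the source data".

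Table 5 marks AE review at end of treatment, 3 months and 6 months. Section 8.4.2 makes the frequency and proportion of adverse events a safety outcome and gives it no time window.

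**The concern.** Section 10.3 names the weakest and the strongest of the three related grades and omits the one between them. Because the list is closed, the omission has an operative effect: a site that grades a non-serious event as probably related has no instruction to log it. Nothing in 10.3 refers the site to the related grouping in Table 7.

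At stake is the completeness of the AE outcome in 8.4.2 and of the safety data supplied to the DMC under section 17.6. Section 10.2 describes recording AEs in the medical notes as routine, but the notes do not fill the AE log, and events not logged at the time are hard to recover later.

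The timing statements raise a lesser question. A site could read the opening sentence of 10.3 together with the later reviews in Table 5 as asking for related AEs up to 6 months, or read the second entry as stopping collection soon after treatment. If sites differ on this, AE counts will not be comparable across centres.

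**Working it through.** The protocol states no figure on this point, so the check is mainly a comparison of sections.

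**Causality grades**

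| Table 7 grade | Grouping in 10.6 | Non-serious AE logged under 10.3? |
|---|---|---|
| Definitely | Related | Yes, within the window |
| Probably | Related | Not listed |
| Possibly | Related | Yes, within the window |
| Unlikely | Unrelated | No |
| Not related | Unrelated | No |

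One of the three related grades has no route to the AE log.

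**Size of the loss.** Let N be the number of non-serious related AEs inside the log window and p the share graded probably. Under literal compliance the log holds N × (1 − p) events. The protocol gives neither N nor p, so p can lie anywhere from 0 to 1. The proportion of participants with an AE need not fall as far as the count, because a participant may have another event that is logged.

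**SAEs.** The first entry in 10.3 has no causality filter, so a serious event graded probably is reportable. The exceptions are in 10.4.1: pre-planned hospitalisation and admissions under 24 hours do not go on the SAE form. If such an event is graded probably related, the second entry in 10.3 does not clearly capture it either.

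**Length of the AE log window.** Inputs: 10 sessions over 10 working days, with treatment starting on the day of randomisation or within 7 days (section 7.1); closure 7 days after treatment (10.3); final follow-up 6 months after randomisation (section 3). Assumptions: 10 consecutive working days span 12 to 14 calendar days; 6 months = 365.25/2 = 182.6 days; 3 months = 91.3 days.

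- Window length: 12 + 7 = 19 days to 14 + 7 = 21 days.
- Closing day after randomisation: 19 to 21 with a same-day start; 26 to 28 with a start 7 days later.
- Share of the time from start of treatment to 6 months: 19/182.6 = 10.4% at the low end; 21/(182.6 − 7) = 12.0% at the high end.
- Gap from closure to the 3-month review: 91.3 − 28 = 63 days to 91.3 − 19 = 72 days.
- Time from closure to 6 months: 182.6 − 28 = 155 days to 182.6 − 19 = 164 days.

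These are shares of calendar time, not of events. They show that the two periods in 10.3 differ greatly, and nothing about how many events fall between them.

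**The case against.** The strongest reply is that the missing grade is a drafting slip. No coherent rule would admit the weaker and the stronger grade and skip the one between, and 10.6 counts all three as related. That is very likely so. A reader might infer that the protocol means to exclude probably related events; the documents do not support that. But sites work from the wording of 10.3, so the slip still needs correcting.

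On timing, the reply largely succeeds. A reader might infer that every treatment-related event after about week 3 is lost, or that the 7-day limit is an error. Neither follows:

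- Serious events remain reportable to the end of follow-up, subject to 10.4.1.
- The limit belongs to a declared targeted-reporting strategy. It fits section 6.6, which names soreness at the patch site, while treatment is given and soon afterwards, as the only risk.
- The 3- and 6-month AE reviews can serve to find SAEs.
- The 4 to 6 months mentioned in section 1.7 refers to when the pain benefit starts to wear off, not to late harm. Sensory worsening is measured separately by quantitative sensory testing, though only in selected centres.

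What stands is that 10.3 never says that the long period is for SAEs and the short one for non-serious related AEs. That reading reconciles the text, but the reader has to supply it.

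**Conclusion.** The point holds for non-serious AEs. As written, 10.3 contradicts Table 7 by omitting one of three related grades from a closed list. Under literal compliance the AE outcome in 8.4.2 would be understated. This conclusion rests on sites following the text as written and on at least some non-serious events being graded probably.

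The size is unknown. A reader might infer that a third of related events are lost because one grade in three is missing, or that most are lost if sites favour that grade for skin soreness. The protocol gives no distribution of events over grades, so neither figure is supported.

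On timing, the finding is limited to an unreconciled statement of periods; the 7-day window is not shown to be wrong. The rule is the same in both blinded arms, and the primary outcome, the sample size and the efficacy analysis are not affected.

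**What to change.** 1. In 10.3, change the second entry to cover AEs possibly, probably or definitely related, with a reference to the Related group in Table 7. Align the AE log instructions with it.
2. Add a sentence to 10.3 stating which period applies to SAEs and which to non-serious related AEs. Make the opening sentence of 10.3, the AE review rows of Table 5 and the outcome in 8.4.2 agree with it. If the short window is kept, 8.4.2 should say that non-serious AEs are counted only within it, and Table 5 should say what the later reviews collect. Extending non-serious collection to the 6-month visit is an alternative; that is a trade-off for the trial team, not a correction the documents require.

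The first change is one word plus a cross-reference. The second is a clarifying sentence with consequential edits. Together they cost a short amendment, revised AE log instructions to sites and perhaps a few more log entries. Extending collection would add more entries.

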7. TRIAL INTERVENTION

7.1 Trial intervention and dosing schedule

FREMS is a non-invasive treatment modality for several chronic painful conditions. The device consists of the FREMS unit (**Figure 1**) including a liquid crystal display with touchscreen, 1 power supply unit and power cable, 1 remote control, electrode connection cables for neuromodulation, electrodes, 1 user treatment key card and 1 connection protection cover.

[figure not shown]
Figure 1: APTIVA FREMS equipment and electrodes positions

During a treatment session, a series of biphasic asymmetric electric sequences of negative pulses with double modulation (frequency and duration) are delivered through disposable electrode pads applied to the skin along the pathway of the nerve involved in the neuropathy. The pulses (**Figure 2**) are characterised by:

- sharp spike and an asymmetrical shape with a peak amplitude variable from 0 V to 255 V
- pulse frequency variable within the range of 0 Hz to 50 Hz
- pulse duration variable within the range of 10 μ s to 40 μ s

Figure 2: An example of FREMS pulse sequence

For PDPN, 8 electrode pads (2 per connection cable) are applied to the calf, shinbone, ankle and midfoot of each leg. At the beginning of each treatment session, the electrical dose is set by the healthcare professional, based on the sensation felt by the patient: the electrical stimulation should be felt but should not be painful. Hence the current is increased gradually till the patient feels it without discomfort and the strength of the current is set at that point. This process is repeated for each individual electrode position separately. The duration of a treatment session is 35 minutes with a treatment cycle comprising 10 daily sessions (two working weeks) as per manufacturer instructions and the previous clinical trials that used FREMS. The device is CE marked and training, including a detailed manual and training video, will be provided prior to the site opening to recruitment. Each site will also be visited by an investigator during the first six months of recruitment at their site to quality check the use of the FREMS machine.

Participants will be randomised to receive:

- FREMS during 10, 35-minute sessions over 10 working days (in addition to standard care).

OR

- TENS during 10, 35-minute sessions over 10 working days (in addition to standard care).

It is expected that treatment will start on the same day as randomisation; if not, treatment must start within 7 days.

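### Related adverse events are reportable for 7 days after treatment ends, but no scheduled enquiry covers that week until the 3-month visit, some 9 to 11.6 weeks later

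*Protocol*

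**What the plan says.** Protocol section 10.3 first sets a general period: "The reporting period for AEs in FREMS-PDPN will be from the start of treatment until the end of trial follow-up". It then adopts targeted reporting. Serious events are reported on their own form. Non-serious events go on an adverse event log only if they are related to trial treatment and fall in a shorter window, "occurring between the start of trial treatment and 7 days after the end of the trial treatment period".

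The schedule of enquiry is in Table 5 (section 9.1). Its adverse event review row is marked at three points: end of treatment, 3 months and 6 months. Section 9 ties the first of these to the last of the ten sessions: "For data collected at visit 10 (End of treatment), please see Table 5". It then goes straight to the follow-up visits: "Visits 11-12: At 3 and 6 months respectively". No visit or call is scheduled in between.

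Two other places matter. Section 6.6 names a single treatment risk, soreness where the patches are applied, and places it during treatment and soon afterwards. Section 8.4.2 lists "Frequency and proportion of Adverse Events" as a safety outcome.

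**The concern.** The protocol defines a window for related non-serious events and then schedules its review at the point where the last 7 days of that window begin. Those 7 days are not asked about until the 3-month visit. They are also when any soreness following session 10 would occur, so part of the one reaction the protocol expects falls in the period without an enquiry.

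At stake is the quality of the adverse event count for that week. Mild, short-lived symptoms are hard to recall after two months or more. They are also hard to date, and here the date decides whether an event is reportable at all. An event on day 6 after the last session counts and one on day 9 does not. A participant asked some ten weeks later may not be able to tell them apart.

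**Working it through.** The protocol states no figure for this interval, so there is none to reproduce. The check is a calendar calculation.

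**Inputs**
- Ten sessions over ten working days (section 7.1).
- Start of treatment (section 7.1): "It is expected that treatment will start on the same day as randomisation; if not, treatment must start within 7 days". The delay is therefore 0 to 7 days.
- The reportable window closes 7 days after the last session (section 10.3).
- The 3-month visit is timed from randomisation (Table 5). I assume it falls on day M = 90 to 92, with randomisation as day 0.
- I also assume a weekday randomisation, a weekday start, and sessions on consecutive working days with no holiday or missed day.

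**Formulas**
- L = day of session 10. A Monday start gives start + 11 days (two full working weeks). A start on Tuesday to Friday crosses two weekends and gives start + 13 days.
- W = L + 7, the day the window closes.
- Shortest delay to enquiry (event on the last day of the window) = M − W.
- Longest delay to enquiry (event just after session 10) = M − L.

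**Results**

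| Treatment start | L | W | M − W | M − L |
|---|---|---|---|---|
| Day of randomisation | 11 or 13 | 18 or 20 | 90 − 20 = 70 to 92 − 18 = 74 days (10.0 to 10.6 weeks) | 90 − 13 = 77 to 92 − 11 = 81 days (11.0 to 11.6 weeks) |
| 7 days later | 18 or 20 | 25 or 27 | 90 − 27 = 63 to 92 − 25 = 67 days (9.0 to 9.6 weeks) | 90 − 20 = 70 to 92 − 18 = 74 days (10.0 to 10.6 weeks) |

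Over all permitted starts, the delay from event to first scheduled enquiry runs from 63 days (9.0 weeks) to 81 days (11.6 weeks). A late 3-month visit would lengthen it. A session postponed to a later day would shorten it.

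**Other routes that might cover the week**
- Section 10.2 describes routine recording in the medical notes. It schedules no contact.
- Table 9 (section 11.1) requires events that a participant reports, including by telephone, to be documented. This is a real route, but a passive one.
- The daily text or email asks only for the pain score (sections 1.7, 9 and 11.3).
- Setting the current at each session (section 7.1) and recording intolerable sensations (section 7.3) involve contact about discomfort, but both end with the last session.

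None of these is an active enquiry in the 7 days after session 10.

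**The case against.** The strongest defence is that this is a deliberate and proportionate choice. Section 10.3 adopts targeted reporting openly and gives its reason, that the safety profile is well characterised. Section 3.2 rates the risk as no higher than standard care. A reporting window does not by itself require a contact on its closing day. The 3-month review still looks back over the week in question, and volunteered events must be documented. Soreness after sessions 1 to 9 arises before visit 10 and is covered by that review. All of this stands and limits the size of the point. None of it provides an enquiry in the week after session 10.

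A reader might infer more than the protocol supports:

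- **That events are under-counted.** This is plausible but not shown. Poor recall can also move an event into the window, so even the direction of error is not certain.
- **That about a third of events are lost.** Counting the first session as day 1, session 10 falls on day 12 or 14 and the window lasts 19 or 21 days, so the tail is 7/19 = 37% or 7/21 = 33% of it. That is a share of days. The share of related events is unknown and may be well below a third, because soreness after the first nine sessions falls outside the tail.
- **That nothing is asked during sessions 1 to 9.** Table 5 has no columns for those sessions, so the absence of a mark shows nothing. Staff adjust the current to the participant's sensation each time, and the visit 10 review looks back only about two weeks.
- **That skin reactions would go untreated.** Adverse event review is data collection. Standard care continues throughout, and the protocol describes no delayed skin harm.
- **That the comparison of arms is biased.** The schedule is identical in both arms, and the protocol gives no ground for a differential effect.

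**Conclusion.** The reporting window and the schedule of enquiry do not match. Related non-serious events in the 7 days after the last session are first actively asked about 9.0 to 11.6 weeks later, and until then capture rests on volunteered reports. Events may be missed or misdated across the 7-day limit.

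The interval depends on the calendar assumptions listed in the working. How many events are affected cannot be derived from the protocol. The point is confined to non-serious related events after session 10. Serious events are reportable to the end of follow-up by a separate route (sections 10.3 to 10.5), and the primary outcome is not touched. It is a minor point, worth raising because the remedy is cheap and improves a listed safety outcome.

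**What to change.** Reconcile Table 5 with section 10.3 by adding one adverse event enquiry to the table, 7 days after the last session attended. Tying it to the last session attended also covers participants who stop treatment early. Send it as one extra yes/no question in the daily REDCap text or email that participants already receive. A yes should prompt the site to contact the participant, establish the date and relatedness, and complete the adverse event log.

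The cost is one additional entry in the schedule, minor database programming, one extra question per participant (at most 356 in all), and some follow-up calls and log entries. No visit is added and clinical management does not change.
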